### 15.11 Final Data

Investigator is responsible for maintaining adequate and accurate source documents from which accurate information is transcribed into the EDC system, which is designed to capture all pertinent data for the registry. Data entry should be completed by Investigator or delegate, as delegated on the Delegation of Authority Log.

Once the data have been reviewed by the CRA, queries may be raised in the EDC system if the data are missing, unclear or contradictory. Once all data is entered and all queries resolved, Investigator will sign the completed data electronically via the Investigator Signature section of the EDC system and the database will be locked. The final data set will be provided to the site by Sponsor for archiving.

### 15.12 Publications

No individual Investigator may publish results from his/her investigational site until after publication of the primary manuscript describing the full population.

The detailed obligations regarding the publication of any data, material results or other information that is generated or created in relation to the registry is set out in the Clinical Trial Agreement between Investigator and Sponsor.

### 15.13 Audit/Inspections

To ensure compliance with relevant regulations, data generated by this registry must be available for inspection upon request by representatives of Sponsor and the IRB/EC for each investigational site.

# SAP Revision History

Version Number	Date	Brief Description of Changes

# List of abbreviations

h	
1	
1	
1	
1	

# 1 Introduction

The purpose of this statistical analysis plan (SAP) is to provide a description of the planned methodology and analysis for Protocol BTG-001653-01 based on protocol version 2.0 dated 09May2018. A mock-up of tables, listings and figures (TLFs) will be provided in a separate document.

### 1.1 Study design

This multicenter, international registry is designed to retrospectively and prospectively collect treatment and outcome data related to pts with submassive (Intermediate-High Risk) or massive (High Risk) PE undergoing the APT treatment. Subjects are treated per Investigator's SoC and in accordance with the IFU. Patients will be categorized according to the APT treatment protocol they received.

Intermediate-High Risk PE will be defined by evidence of RV dysfunction (RV/LV  $\geq$  1.0), hemodynamic stability (normal systemic arterial blood pressure >90 mmHg), and Troponin elevation. High Risk PE will be defined by hemodynamic instability (normal systemic arterial blood pressure <90 mm Hg and/or use of vasopressors).

Retrospective case data will consist of treatment and health outcomes of consecutive patients treated with APT between January 2014 and one year prior to date of site activation.

Prospective subject data will consist of treatment and health outcomes of treated subjects since the site was activated to participate in the registry. For each treated subject enrolled, participation in the registry lasts approximately 12 months. Subjects should be followed per Investigator's SoC. Data will be collected for any echocardiograms and CTAs completed. At minimum, a health status check should be performed at 3 and 12 months. For patients with an abnormal echocardiogram post-APT treatment, an on-site visit with echocardiogram should be performed at 3 months to assess for chronic pulmonary hypertension. An echocardiogram at 12 months is also requested for all patients. Safety data should be reported through 12 months post-index procedure.

#### 1.1.1 Data collection schedule and assessments - Prospective\*\*

Assessments will be performed per Investigator's SoC and collected according to the schedule below. Assessments marked with an asterisk (\*) pertain to an outcome measure or eligibility.

	Baseline	Procedure/Post Procedure	Foll	ow-up
Assessment	Day -1	Day 0 thru Discharge	3 Months (±14 Days) Post APT (Phone or Visit)	12 Months (±1 Month) Post APT (Phone or Visit)
Informed Consent	Χ*			
Demographics	Χ*			
Medical history, risk factors	Χ*			
Vital signs 	Χ*	Х		
Physical Examination	Х			
СТА	Χ*	X*  (if collected)		
sPESI	Х			
APT Procedure		Х		
Echocardiogram 	Х*	X  (if collected)	X* (if collected)	X* (if collected)
Quality of life surveys 		X*	X*	Χ*
Laboratory tests 	Xe	Х		
Biomarkers 	Χ*	Х		
Adverse/VTE/Bleeding Events		X*	X*	X*
Anticoagulation medications	Х	Х	Х	Х

1. Record heart rate, blood pressure, respiratory rate, oxygen saturation vital signs at admission, at start and end of treatment, and once at same time each day of hospitalization

2. Includes RV/LV ratio, TAPSE, estimated RVSP, and collapse of the inferior vena cava (IVC) with respiration. Echocardiograms collected throughout the follow up period will be slotted by months from index procedure for analysis.

3. Collect 24 – 48 hours after the start of the APT procedure

4. PEmb-QOL and EQ-5D-5L

5. Hemoglobin (Hgb), hematocrit (Hct), platelet count, creatinine, activated partial thromboplastin time (aPTT), partial thromboplastin time (PT), and international normalized ratio (INR)

6. Record if collected within 48 hours prior to the start of APT procedure

7. Troponin, brain natriuretic peptide (BNP)/NT-proBNP, lactate/lactic acid, and D-dimer

\*\* For the retrospective portion of the study, data will be collected as available for 12 months post- index treatment and where possible according to the schedule above.

# 1.2 Study objectives

The objectives of this registry are:

- To understand the APT treatment protocol used as SoC across institutions and document changes in practice following the OPTALYSE PE study results
- To describe the effects of varied APT protocols on long-term patient outcomes

#### 2 Statistical methods and analysis

#### 2.1 General methodology and definitions

Continuous data will be summarized with means, medians, standard deviations, minima and maxima, unless otherwise specified. Categorical data will be summarized with observed counts and percentages for each category.

All data collected from the eCRF and derived variables will be provided in listings in addition to the summaries described below.

Baseline is defined as the last non-missing assessment prior to the start of APT treatment.

Windowing rules provided below will be used to assign visits to each follow-up assessment for the retrospective and prospective portions of the study. If multiple assessments occur within the same window, the assessment closest to the middle of the "within schedule window" will be used.

Quality of life surveys will be assigned according to the windows: 3 Months (±14 Days) post-APT procedure and 12 Months (±1 Month) post-APT procedure. Echocardiograms will be slotted by month post-APT procedure.

# 2.2 **Populations**

Safety Population (SP) - The SP will be defined as all patients who receive the APT procedure. Safety and effectiveness summaries will be reported for the SP.

Efficacy Population (EP) - The EP will be defined as all patients who meet eligibility criteria. An additional effectiveness summary will be reported for the EP.

# 2.2.1 Subgroups

Efficacy and safety outcome measures will be summarized separately for the following subgroups:

- APT dose received (ie, >24mg; 20.1-24mg; 12.1-20mg; 4-12mg; <4mg)
- Submassive and massive PE

- Region
- Retrospective and prospective portions of the registry

## 2.3 Disposition, Demographics, Baseline

#### 2.3.1 Disposition

Patient disposition will be summarized for all patients and separately by retrospective and prospective portions of the registry, as well as by SP and EP. The following categories will be summarized:

- Number of patients screened
- Number and percentage of patients who were enrolled and treated
- Number and percentage of patients with 3- and 12-month follow-up
- Number and percentage of patients who discontinued
- Reasons for discontinuation
  - Withdrew consent
  - o Lost to follow-up
  - o Death
  - o Study discontinued by sponsor
  - $\circ$  Other
- Number and percentage of patients who completed the study
- Duration on study (months)

Additionally, listings of inclusion/exclusion criteria, disposition, reason for discontinuation and completion will be provided.

# 2.3.2 Demographic and Baseline Characteristics

Demographic and baseline characteristics are collected at screening. Descriptive summaries and/or listings will be summarized for all patients and separately by retrospective and prospective portions of the registry, as well as by SP and EP. The number and percent ages (categorical variables) and descriptive statistics (continuous variables) will be summarized for the following:

#### **Demographic:**

- Age (years)
- Gender (Male, Female)
- Race (American Indian or Alaska Native, Asian, Black or African American, Native Hawaiian or Other Pacific Islander, White, Other, Not reported)
- Ethnicity (Hispanic or Latino, Not Hispanic or Latino, Not reported)

#### **Baseline characteristics**

- Physical examination
- Medical history

- Clinical risk factors including pertinent PE history
- sPESI
- Anatomic location of PE
- Anticoagulation medications

#### 2.3.3 Protocol deviations

The number and percentage of patients with informed consent or eligibility protocol deviations will be summarized. Additionally, a listing of deviations will also be presented.

#### 2.4 Treatment and other medication and therapies

#### 2.4.1 Study treatment

The following APT procedure details will be summarized:

- Location of PE
- Access route
- Fluoroscopy time
- Volume of Contrast
- Ultrasound guidance?
- Time for placement of catheters (h)
- Ultrasound (h)
- Total dose/total dose per catheter
- Technical/procedural deviations
- Frequency of adjunctive therapies following APT

Patients will be categorized according to the thrombolytic dose they received. The following categories will be used:

- >24mg
- 20.1-24mg
- 12.1-20mg
- 4-12mg
- <4mg

For each category, the mean, min, and max time will be summarized. Frequency of each of the APT categories will be summarized with observed counts and percentages for each category overall, by analysis population, by region, and by the retrospective and prospective portions of the registry.

Frequency of use of each of the APT treatment protocols before and after OPTALYSE PE results were made public will also be summarized and compared using fisher's exact test.

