## **13. STATISTICAL CONSIDERATIONS**

### **13.1 Statistical Analysis**

The statistical analysis plan (SAP) will be a separate document finalized prior to data analysis. The SAP will be updated as required, in association with any protocol amendments. The plan will include detailed descriptions of analysis methods, tables, listings and figures and will describe statistical programming considerations.

For descriptive statistics, continuous data (e.g., age) will be summarized with n, mean, median, standard deviation, minimum and maximum and categorical data (e.g., gender) will be summarized with observed counts and percentages for each category.

Patients will be analyzed according to the APT treatment protocol they received (i.e. duration of treatment and dose, type of fluid received). Frequency of use of each of the APT treatment protocols before and after OPTALYSE PE results were made public will be summarized and compared using fisher's exact test.

Each outcome measure will be summarized for the full registry population as well as separately by the different APT treatment protocols, including 95% confidence intervals. Additionally, outcome measures will be summarized by the following subgroups: submassive and massive PE, each region, and by the retrospective and prospective portions of the registry.

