### **13.6 Measurement of APT treatment**

APT treatment and procedure details will be summarized. Patients will be analyzed according to the APT treatment protocol they received (e.g., >6h/>24mg; 6h/12-24mg; 6h/6-12mg; 4h/4-8mg; 2h/4-8mg, other). Frequency of use of each of the APT treatment protocols before and after OPTALYSE PE results were made public will be summarized and compared using fisher's exact test.

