### **13.7 Efficacy Outcome Measures Analyses**

Descriptive statistics will be used to summarize efficacy outcome measures RV/LV, TAPSE, IVC Collapse, estimated RVSP and pulmonary arterial pressure by time point and/or study visit including change from baseline for continuous endpoints.

Each efficacy outcome measure will be summarized for the full registry population as well as separately by the different APT treatment protocols, including 95% confidence intervals. Additionally, efficacy outcome measures will be summarized by the following subgroups: submassive and massive PE, each region, and by the retrospective and prospective portions of the registry.

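### The SAP groups patients by thrombolytic dose alone, so its outcome tables cannot separate APT regimens that the protocol distinguishes by treatment duration

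*SAP*

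**What the plan says.** Protocol 13.1: "Patients will be analyzed according to the APT treatment protocol they received (i.e. duration of treatment and dose, type of fluid received". The same section asks for each outcome by treatment protocol with confidence intervals, and Protocol 13.7 repeats this for efficacy: "as well as separately by the different APT treatment protocols, including 95% confidence intervals". Protocol 13.6 illustrates the categories with joint duration-and-dose cells: "e.g., >6h/>24mg; 6h/12-24mg; 6h/6-12mg; 4h/4-8mg; 2h/4-8mg, other".

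SAP 1.1 starts in line with this: "Patients will be categorized according to the APT treatment protocol they received". SAP 2.4.1 then says "Patients will be categorized according to the thrombolytic dose they received" and lists five bands: >24, 20.1-24, 12.1-20, 4-12 and <4 mg. SAP 2.2.1 makes these bands the treatment subgroup. SAP 2.5 (efficacy), 2.6 (additional outcomes) and the general sentence in 2.7 (safety) refer to the 2.2.1 subgroups.

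Duration appears in the SAP only as a procedure summary (ultrasound hours) and as mean, minimum and maximum time within each dose band. Fluid type is not a subgroup. SAP 2.4.1 lists both total dose and dose per catheter, without saying which one defines the bands. Its Fisher's exact test, before and after OPTALYSE PE results became public, refers to APT treatment protocols, a term the SAP does not define.

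**The concern.** The second objective in both documents is to describe how varied APT protocols affect long-term outcomes. Duration is central to that: Protocol 4.3 links shorter treatment as well as lower dose to less bleeding and lower ICU and hospital costs, and two of the OPTALYSE PE regimens (8 mg over 2 h and over 4 h) differ in duration only. A table by dose band gives these two regimens one row. Time summarised within a band describes that row but does not attach outcomes to durations.

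The first objective, change in practice, is at risk only conditionally. If the Fisher test is run on the dose bands, a centre that shortens treatment without leaving its band shows no change.

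**Working it through.** The plan gives no figure to reproduce. The check maps the regimens named in the documents onto the SAP bands.

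**Inputs.** Bands from SAP 2.2.1 and 2.4.1; categories from Protocol 13.6; from Protocol 4.3, the four OPTALYSE PE regimens, the earliest reported course (about 22 mg over 25 h) and later practice of 0.5 to 1 mg/h per catheter over an average of 18 h. One or two catheters is an assumption.

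**1. OPTALYSE PE regimens and the earliest course.** The per-catheter column assumes that the quoted doses are totals split equally over two catheters.

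| Regimen | Band on total dose | Dose per catheter | Band per catheter |
|---|---|---|---|
| 8 mg/2 h | 4-12 | 4 mg | 4-12 |
| 8 mg/4 h | 4-12 | 4 mg | 4-12 |
| 12 mg/6 h | 4-12 | 6 mg | 4-12 |
| 24 mg/6 h | 20.1-24 | 12 mg | 4-12 |
| 22 mg/25 h | 20.1-24 | 11 mg | 4-12 |

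Of the six pairs of OPTALYSE PE regimens, three share a band on total dose and all six do per catheter.

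**2. Protocol 13.6 categories, total dose.** 2h/4-8mg, 4h/4-8mg and 6h/6-12mg lie wholly in 4-12 mg. 6h/12-24mg is split over 12.1-20 and 20.1-24 mg, with exactly 12 mg falling in 4-12 mg. >6h/>24mg maps to >24 mg. So three of the five named categories collapse into one band.

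**3. What merging hides.** Protocol 4.3 reports 48 h RV/LV changes of -0.22, -0.25 and -0.18 for the three regimens sharing 4-12 mg on total dose. A pooled row shows one value between -0.18 and -0.25, set by the regimen mix; at equal weights it is (-0.22 - 0.25 - 0.18)/3 = -0.65/3 = -0.217. No standard deviations are given, so these differences may be noise. The example shows the mechanism, not a demonstrated loss.

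**4. Before/after comparison, only if it uses the bands.** Total dose = rate × catheters × 18 h:

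- 0.5 × 1 × 18 = 9 mg (4-12)
- 0.5 × 2 × 18 = 18 mg (12.1-20)
- 1 × 1 × 18 = 18 mg (12.1-20)
- 1 × 2 × 18 = 36 mg (>24)

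Moving each of these four cases to each of the four OPTALYSE PE regimens gives 4 × 4 = 16 moves.

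- *Total dose:* only the 9 mg case can stay in its band, on moving to 8 mg/2 h, 8 mg/4 h or 12 mg/6 h. That is 3 of 16.
- *Per catheter, same number of catheters before and after:* the starting doses are 9, 9, 18 and 18 mg. The one-catheter 9 mg case stays in band for 3 regimens (8, 8 and 12 mg) and the two-catheter 9 mg case for 4 (4, 4, 6 and 12 mg). The 18 mg cases never stay. That is 7 of 16.

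The documents do not say how common any of these moves is.

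**The case against.** The strongest counter-argument is about versions. The SAP is "based on protocol version 2.0 dated 09May2018", while the supplied protocol cites a July 2018 article, so the SAP may have matched an earlier protocol text. The documents cannot settle this. It would explain the mismatch but not remove it, since Protocol 13.1 also says "The SAP will be updated as required, in association with any protocol amendments".

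Second, the 13.6 list is introduced as examples and methods are left to the SAP. That permits other cut-points. It does not permit dropping duration, which 13.1 gives as part of what a treatment protocol is.

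Third, duration is summarised, all data are listed, and "A mock-up of tables, listings and figures (TLFs) will be provided in a separate document"; that document was not available. Neither time per band nor listings yield outcomes by duration, and shells should follow a definition in the SAP rather than supply one.

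Several points on size do stand:

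- On total dose the bands separate 24 mg/6 h, the regimen with the largest RV/LV change (-0.32), and 13 of the 16 moves do change band.
- Only one pair of named 13.6 categories differs by duration alone.
- The RV/LV example is a 48 h measure, whereas the objective concerns long-term outcomes.
- The 22 mg/25 h course comes from the earliest study, and nothing shows that it occurs in the registry.
- Total dose is the more natural reading of the SAP sentence, so the per-catheter results are a second scenario.
- The four adverse-event summaries by subgroup in SAP 2.7.1.3 are introduced as additional and need not limit the general sentence in 2.7.

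**Conclusion.** The point holds and should be fixed before analysis. The SAP's regimen tables cannot give outcomes by treatment duration, which Protocol 13.1 requires and the second objective needs. This follows from the text alone and needs no assumption about regimen frequencies.

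Its reach depends on an unstated choice. On total dose, three of four OPTALYSE PE regimens and three of five named 13.6 categories share one band. On dose per catheter, with doses split equally over two catheters, all four OPTALYSE PE regimens do. The effect on the first objective is conditional on the Fisher test using the dose bands. How many patients are affected, and whether outcomes differ by duration within a band, cannot be told from the documents.

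**What to change.** In SAP 2.2.1 and 2.4.1, define APT treatment protocol by mutually exclusive, exhaustive dose-by-duration categories, reconciled with Protocol 13.1 and 13.6. The 13.6 list should not be copied unchanged: 12 mg/6 h fits two of its cells, and courses over 6 h at 24 mg or less (22 mg/25 h and three of the four 18 h cases above) fit only its residual category.

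One analysis grouping that works, offered as an illustration, has seven levels:

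1. up to 2 h
2. >2-4 h
3. >4-6 h, up to 12 mg
4. >4-6 h, >12 mg
5. >6 h, up to 24 mg
6. >6 h, >24 mg
7. fluid not comparable in mg

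The four OPTALYSE PE regimens fall in levels 1 to 4. Levels 1 and 2 do not split by dose, which the team may wish to refine. A row for unrecorded dose or duration is also needed, because missing values are not imputed.

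The SAP should also:

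- state a tolerance at 2, 4 and 6 h, so that a 6 h course recorded as 6.1 h is not classed as over 6 h;
- state whether dose is total or per catheter;
- use the same categories for the outcome tables and the Fisher comparison;
- list the safety outcomes shown by category (major bleeding is not among the four summaries in 2.7.1.3);
- give the OPTALYSE PE cut date, since the protocol references show a 2017 congress presentation and a July 2018 article;
- keep the dose bands as a secondary display, and update the protocol version it cites.

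The cost is SAP wording and table shells. Ultrasound hours and total dose are already planned summaries. Infusion hours are not named in either document, so the eCRF must be checked before they are used. The downside is sparser cells: at the caps of 1000 retrospective and 500 prospective patients, seven levels average 1500/7 = 214 patients against 1500/5 = 300 for five bands. In the prospective part the averages are 500/7 = 71 against 500/5 = 100. Uneven use will leave some levels much smaller.

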to ultrasound during lytic treatment using r-tPA. These effects were seen at the frequencies produced by the EKOS catheter. The time of clot treatment in the studies was 30 minutes. From these studies, we postulate that r-tPA in the presence of ultrasound will produce significant fibrinolysis within 2 hours of receptor binding and may continue for another 7 to 12 hours after the APT Procedure is complete. Thus, thrombus burden may be significantly reduced within a few hours of the APT Procedure to restore pulmonary perfusion, reduce RV dilatation, and decrease pulmonary artery pressures.

The earliest study of the APT procedure in PE demonstrated that doses of approximately 22 mg r-tPA delivered with the APT procedure over 25 hours were effective in treating PE in subjects suffering from massive PE. Since that time, doses used in treating PE have ranged from 0.5 to 1 mg/hr/catheter delivered over an average of 18 hours, with no infusion duration being less than 12.9 hours (excluding one subject). Even though efficacy measurements have been made at 24 and 48 hours, clinicians have reported subjects often improve within a few hours of the start of treatment. These observations, along with the aforementioned pharmacology studies, provide evidence to support the scientific rationale for investigating the reduction in ultrasound - r-tPA treatment time.

The OPTALYSE PE study was designed to investigate the lowest r-tPA dose-ultrasound treatment time required to achieve the same reductions in thrombus burden and associated improvement in physiologic parameters demonstrated in ULTIMA and SEATTLE II. Results of the OPTALYSE PE study were intended to inform the study design for further studies of the APT procedure. Analysis of the first 100 evaluable subjects in the U.S. study suggested equipoise between each study arm and therefore a sample size was extended to additional sites in the U.K. Improvement in the RV/LV diameters by core laboratory-assessed echocardiographic reads were -0.17, -0.17, -0.12, and -0.29 at 4 hours and -0.22, -0.25, -0.18, and -0.32 at 48 hours in patients randomized to 8 mg/2 hrs, 8 mg/4 hrs, 12 mg/6 hrs, and 24 mg/6 hrs, respectively. Improvement in modified Miller score was also seen in all groups.

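### The SAP's mg bands ignore infusion time and number of catheters, so they do not identify the APT treatment protocol a patient received

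*SAP*

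**What the plan says.** SAP 2.4.1 sets the rule: "Patients will be categorized according to the thrombolytic dose they received". SAP 2.2.1 uses the same cut-points to define an outcome subgroup: "APT dose received (ie, >24mg; 20.1-24mg; 12.1-20mg; 4-12mg; <4mg". SAP 2.5, 2.6 and 2.7 carry that subgroup into the efficacy, additional and safety outcomes.

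Two related quantities appear in SAP 2.4.1 but do not form the bands. Among the procedure details it lists "Total dose/total dose per catheter", and of infusion time it says only "For each category, the mean, min, and max time will be summarized". The same section then plans a Fisher's exact test on the frequency of APT treatment protocols before and after the OPTALYSE PE results. The mg bands are the only categories the SAP defines.

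The protocol describes regimens differently. Protocol 13.1 defines an APT treatment protocol by duration, dose and type of fluid. Protocol 13.6 gives example categories of duration plus dose: ">6h/>24mg; 6h/12-24mg; 6h/6-12mg; 4h/4-8mg; 2h/4-8mg, other". On practice before OPTALYSE PE, Protocol 4.3 says "doses used in treating PE have ranged from 0.5 to 1 mg/hr/catheter delivered over an average of 18 hours". It gives the OPTALYSE PE arms as "8 mg/2 hrs, 8 mg/4 hrs, 12 mg/6 hrs, and 24 mg/6 hrs", without a number of catheters. Dosing in the registry itself is left to the treating physician (Protocol 9.1.1).

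**The concern.** The objectives (Protocol 5.1, SAP 1.2) are to document how APT practice changed after OPTALYSE PE and to describe outcomes under different APT protocols. Both need categories that correspond to regimens. A band cut on mg alone fails in two ways. It can place one regimen in two bands according to how many catheters were used, and it can place different regimens in one band.

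In the before/after comparison, a shift between one and two catheters would then move patients across bands with no change in dose per catheter or duration. In the outcome tables, a band would not correspond to any APT protocol a reader could name. The catheter part of this remains among patients with the same infusion time and the same drug, so it is not only a matter of the missing duration.

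**Working it through.** The plan gives no figure behind the bands, so there is nothing to reproduce. The check maps regimens onto the bands.

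**Inputs**
- Rate r: 0.5 and 1 mg per hour per catheter (Protocol 4.3).
- Hours h: 18, the average; 12.9, the shortest apart from one subject; 25, from the earliest study (all Protocol 4.3).
- Number of catheters k: 1 or 2. This is an assumption; the documents give no distribution.
- Bands: SAP 2.2.1.

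**Step 1. Per-catheter dosing.** Total dose D = r × h × k.

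| r (mg/h/catheter) | h | D, k = 1 | band | D, k = 2 | band |
|---|---|---|---|---|---|
| 0.5 | 12.9 | 6.45 mg | 4-12 | 12.9 mg | 12.1-20 |
| 0.5 | 18 | 9 mg | 4-12 | 18 mg | 12.1-20 |
| 1 | 12.9 | 12.9 mg | 12.1-20 | 25.8 mg | >24 |
| 1 | 18 | 18 mg | 12.1-20 | 36 mg | >24 |
| 1 | 25 | 25 mg | >24 | 50 mg | >24 |

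At 18 hours both rates split by number of catheters. The 12.1-20 mg band pools 0.5 mg/h with two catheters and 1 mg/h with one (18 mg each). The last row shows a case that does not split.

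**Step 2. Protocol 13.6 categories.**
- 6 h, 12-24 mg: 12 mg falls in 4-12, doses from 12.1 to 20 mg in 12.1-20, and doses from 20.1 to 24 mg in 20.1-24. That is three bands.
- 6 h, 6-12 mg; 4 h, 4-8 mg; 2 h, 4-8 mg: all in 4-12. That is three categories in one band.

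This step needs no assumption about catheters beyond reading the mg figures as totals.

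**Step 3. OPTALYSE PE regimens.** As stated, 8 mg/2 h, 8 mg/4 h and 12 mg/6 h all fall in 4-12, and 24 mg/6 h falls in 20.1-24. The split depends on what the stated figures mean:
- If they are two-catheter totals, one catheter gives 4, 4, 6 and 12 mg, all in 4-12. Only 24 mg/6 h changes band.
- If they are per catheter, two catheters give 16, 16, 24 and 48 mg (12.1-20, 12.1-20, 20.1-24, >24). All four change band.

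**Step 4. The obvious repair.** Suppose the present cut-points were applied to dose per catheter. On the two-catheter reading the four regimens become 4, 4, 6 and 12 mg per catheter, all in 4-12. The split goes, but the overlap gets worse.

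**Step 5. Illustration with assumed shares.** Take a fixed regimen of 12 mg per catheter over 6 h: 12 mg (4-12) with one catheter, 24 mg (20.1-24) with two. Let two-catheter use rise from 70% to 80%. Use the normal approximation for two proportions at two-sided 5%, power = Φ[(0.10 − 1.96·SE₀)/SE₁], with pooled share (2 × 0.70 + 0.80)/3 = 0.733.
- 200 before, 100 after: SE₀ = √(0.733 × 0.267 × 0.015) = 0.0542; SE₁ = √(0.21/200 + 0.16/100) = 0.0515; power about 45%.
- 1000 before, 500 after: both standard errors are divided by √5, to 0.0242 and 0.0230; power about 99%.

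So a test on the bands could well report a change although dose per catheter and duration stayed the same. The shares and the group sizes are invented for illustration.

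**The case against.** The strongest reply has five parts.

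1. *The SAP never says total.* True. It lists total and per-catheter dose and names neither as the banding variable. Total is the natural patient-level reading, but a reader who took it as stated would go beyond the text. The gap itself needs closing, because the choice alters the banding dose two-fold for a two-catheter patient.

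2. *Per-catheter dosing is documented only for past practice.* Also true. The protocol's regimen definitions and the OPTALYSE PE arms carry no catheter unit. A reader might infer that the two-fold ranges in Protocol 13.6 stand for one versus two catheters, since their upper ends equal the OPTALYSE PE doses. That fits, but nothing there says so.

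3. *Catheter count as a marker of disease.* A reader might infer that more catheters means more extensive clot, so that a pattern of outcome by dose could arise from disease extent alone. No passage links the two. It is an assumption, and the point does not need it.

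4. *The Fisher test may not use the bands.* The SAP sentence speaks of treatment protocols, not of dose categories. This stands as far as it goes, but the SAP defines no other categories. More drug through a second catheter is also arguably a change in practice in its own right. That favours showing it separately from a change of regimen.

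5. *The outcome tables are descriptive, and per-catheter dose, time and location of PE are summarised.* This softens the consequence. It does not remove it, because per-catheter dose and time do not define the bands, the subgroups or any stated category for the test.

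**Conclusion.** The point holds in limited form. The mg bands do not identify the APT treatment protocol as Protocol 13.1 and 13.6 describe it. With the per-catheter dosing in Protocol 4.3 at 18 hours, both ends of the rate range change band between one and two catheters, and one band holds two rates. One protocol category covers three bands, and three categories share one.

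It would be too strong to say that every regimen splits. Among the four OPTALYSE PE regimens the count is one if the stated doses are two-catheter totals and four if they are per catheter; the documents do not settle which. The overlap of three of these regimens in 4-12 mg holds on the doses as stated. The size of any distortion in the before/after comparison cannot be known from the documents, because they give neither the catheter distribution nor its change over time.

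This is an inexpensive improvement to the analysis categories. It passes no judgement on any dose or regimen.

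**What to change.** - In SAP 2.2.1 and 2.4.1, state that the five mg bands use total dose. Keep them as an exposure summary, for example for the bleeding tables.
- For regimen frequency, the Fisher before/after comparison and the outcome subgroups, use the duration-plus-dose categories of Protocol 13.1 and 13.6, and say how type of fluid enters.
- Cross-tabulate these tables by number of catheters (one, two), with dose per catheter shown.
- Do not apply the present cut-points to dose per catheter, for the reason in Step 4.
- Reconcile the protocol categories with the SAP before using them. As listed, 12 mg over 6 h belongs to both 6-hour categories. An infusion longer than 6 h with 24 mg or less, such as the 9 and 18 mg totals at 18 hours, fits none of the named categories and would go to the residual one.

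No new type of data is needed: SAP 2.4.1 already plans to summarise time and dose per catheter, which presupposes the catheter count. The cost is SAP wording, re-cut tables and some smaller cells.
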